3.2 Purpose of Study/Potential Impact

The goal of the proposed study is to determine if the sensory irritation (a marker of potential toxicity) of commercial e-liquids containing aldehydes compared to a control non-aldehyde

containing e-liquid, can be reduced by increasing their water content without adversely affecting flavor appeal in adult e-cigarette users. Given that adding water to e-liquid is an innocuous manipulation, if irritation is reduced and effect on appeal is limited, this could be a tool for regulation to reduce harm associated with e-cigarettes.

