(4) Flavor Exposure: We will expose participants to four different e-liquids flavors; cinnamon, cherry, vanilla, and grape e-liquid. All e-liquids are commercially available currently, except for the cinnamon e-liquid, which is currently only available for research use. This cinnamon e-liquid was developed to mirror commercially available cinnamon products. Cinnamon flavoring is known to have health impacts at levels much higher than participants will be exposed to in this study.²¹ We are not aware of any effects from the other flavors being used in this study but participants will be told that if they feel any adverse events or want to stop they are free to do so. Additionally, we will exclude anyone that reports allergies to any of the four flavors used. In the consent form, we will not state the flavors being used, but will note that one flavor is not currently commercially available.

(5) Urine/Saliva Collection: Urine/saliva collection at intake and during the study for females and should add no risks other than those normally associated with these procedures.

(6) Rating Scales and Assessments: These are all noninvasive and should add no risk. The major disadvantages are the time taken to complete them, and possible breach of confidentiality. Our past experience with these measures indicates that they are acceptable to subjects.

(7) Limits to confidentiality: All participants will be specifically told that we will not reveal any personal information collected as part of the research procedures, including their reported use of e-cigarettes and other substance use history. However, there is always the possibility that participation in this study may make others, such as friends and family members, aware of their tobacco use status. They will be told that if they do not feel comfortable with this, then they should not participate in the project. They will also be told that if they report any information to us about abuse or homicidal/suicidal behavior, we will be required to report this information to the appropriate authorities.

Protections Against Risk: We will reduce risks by:

- Requiring participants to be regular nicotine & flavor e-cigarette users.
- Administering briefest possible exposure needed for our outcomes to each study product (2 e-cigarette puffs/product)
- Using well-defined inclusion/exclusion criteria to rule out participants with pre-existing medical conditions

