4.2 Primary Objective

The primary objective of this study is to examine whether (a) sensory irritation and (b) appeal are decreased in e-liquids containing flavor aldehydes (i.e. vanilla, cherry, cinnamon) compared to e-liquids not containing flavor aldehydes (i.e. grape) when the water concentration is increased from the baseline water concentration to the following levels; 5% total water volume, 10% total water volume, 20% total water volume.

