6.1 Treatment

6.1.1 Identity of Investigational Product

The investigational tobacco products being used in the study are the following e-liquids in 36mg nicotine salt concentration: (1) DuraSmoke Red Label (50/50 propylene glycol/vegetable glycerin base) Cherry flavor liquid, (2) DuraSmoke Red Label ((50/50 propylene glycol/vegetable glycerin base) Vanilla flavor liquid, (3) DuraSmoke Red Label ((50/50 propylene glycol/vegetable glycerin base) Grape flavor liquid, and (4) American E-liquids Store (50/50 propylene glycol/vegetable glycerin base) Cinnamon Flavor Liquid. All of these products will be administered in a Suorin iShare Pod System E-cigarette. All of these products are currently commercially available, except American E-liquids Store (50/50 base) Cinnamon Flavor Liquid, which is currently only available as a research product. However, this flavor was a previously commercially available e-liquid and was developed the formulation has not changed. It is not currently sold by American E-Liquids due to lack of popularity. In the current study, these e-liquids will be manipulated by adding water to each product, so that water concentration in each of the four flavors equals the following amounts; (1) 5% of the total e-liquid concentration, (2) 10% of the total e-liquid concentration, (3) 20% of the total e-liquid concentration. Additionally, e-liquids will be presented without added water. Participants will sample (i.e. take 2 directed puffs of each) the four flavors unaltered and in each of the listed water dilutions in randomized order. FDA has reviewed the proposed use of the products and does not have concerns with the use of the investigational tobacco products as described in the protocol. FDA issued a No Concerns letter to Investigators on 2/3/22.

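### Neither the primary nor the secondary analysis shows whether an aldehyde result depends on cinnamon, the one flavor not currently sold and under a different label from the grape control

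*Combined protocol and SAP*

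**What the plan says.** Section 3.2 gives the goal as to "determine if the sensory irritation (a marker of potential toxicity) of commercial e-liquids containing aldehydes" relative to a non-aldehyde control. Sections 2.2 and 3.1 also state the goal for commercial e-liquids. The primary objective (section 4.2) sets "e-liquids containing flavor aldehydes (i.e. vanilla, cherry, cinnamon) compared to e-liquids not containing flavor aldehydes (i.e. grape").

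Section 6.1.1 lists cherry, vanilla and grape as DuraSmoke Red Label products and cinnamon as an American E-liquids Store product. Section 3.2.1 says: "All e-liquids are commercially available currently, except for the cinnamon e-liquid, which is currently only available for research use". Section 6.1.1 adds: "It is not currently sold by American E-Liquids due to lack of popularity".

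The origin of cinnamon is described in two ways. Section 3.2.1 says "This cinnamon e-liquid was developed to mirror commercially available cinnamon products". Section 6.1.1 says "However, this flavor was a previously commercially available e-liquid and was developed the formulation has not changed".

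For analysis, section 6.5.1 plans mixed models with water concentration as the within-subject factor and takes a significant main effect of condition as support for the hypothesis. It names no flavor term, aldehyde-by-water term or contrast with grape. Section 6.5.2 takes flavor as the within-subject factor at each water level separately. No analysis without cinnamon is planned.

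**The concern.** One of the three flavors on the aldehyde side is not on the market at present, and it is the only one whose comparison with grape also crosses labels. If the three are summarised together, an irritation benefit found only in cinnamon could be reported as a benefit for commercial aldehyde e-liquids in general. A benefit in cherry and vanilla could equally be diluted by a cinnamon product that does not respond. Section 3.2.2 says the results could inform a mandate on minimum water content, so readers will want to know which products carried the effect. The planned models do not answer that directly.

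**Working it through.** **Inputs from the documents.** Four flavors at four water levels give 16 cells (section 6.1.4). N is 30 and alpha is 0.05, two-sided (section 6.4.2). No SD, numeric effect size or within-subject correlation is given, so there is no power figure to reproduce.

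**Assumptions.** Each flavor's change from unaltered to a given water level has SD 1. Any two flavors' changes correlate at a common ρ, taken from 0 to 0.8. Data are complete, and the test is a single paired t-test. The three-flavor contrast is the equal-weight mean of the aldehyde changes minus the grape change. The plan does not define this contrast; it is inferred from the objective.

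**Step 1: cinnamon's share.** Aldehyde cells are 3 × 4 = 12, of which 4 are cinnamon: 4/12 = one third. At N = 30 that is 120 of 360 aldehyde ratings per scale.

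**Step 2: can cinnamon alone produce a significant contrast?** If only cinnamon changes, by b, the contrast equals b/3. Its SD per participant is √[(1+2ρ)/3 + 1 − 2ρ] = √[4(1−ρ)/3], which is 1.155 at ρ = 0. Noncentral-t power at n = 30:

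| b (SD) | Contrast b/3 | Standardised, ρ = 0 | Power, ρ = 0 | Power, ρ = 0.5 |
|---|---|---|---|---|
| 0.8 | 0.27 | 0.23 | 0.23 | 0.41 |
| 1.0 | 0.33 | 0.29 | 0.33 | 0.58 |
| 1.5 | 0.50 | 0.43 | 0.63 | 0.90 |
| 2.0 | 0.67 | 0.58 | 0.86 | 0.99 |

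**Step 3: can cinnamon dilute an effect?** If cherry and vanilla change by 0.8 SD and cinnamon and grape do not, the contrast is (0.8 + 0.8 + 0)/3 = 0.53. At ρ = 0, power is 0.69, against 0.96 if all three aldehyde flavors change by 0.8. Full cancellation would need cinnamon to move in the opposite direction by twice the change in each of the other two.

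**Step 4: precision without cinnamon.**
- *Contrast with grape.* The variance with two flavors is (1+ρ)/2 + 1 − 2ρ = 3(1−ρ)/2. The ratio of standard errors is √[(3/2)/(4/3)] = √1.125 = 1.061, whatever ρ is: about 6% larger.
- *LHS change from unaltered, no grape term.* The ratio is √{[(1+ρ)/2] / [(1+2ρ)/3]}. At ρ = 0 it is √(0.500/0.333) = 1.22. At ρ = 0.8 it is √(0.900/0.867) = 1.02. The increase is therefore about 2% to 22%.
- *Feasibility.* If cherry and vanilla each change by 0.8 SD and grape does not, power for the restricted contrast with grape is 0.93 at ρ = 0 and higher with correlation.

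**The case against.** The strongest reply is that cinnamon is close enough to a commercial product. The goal says commercial, not currently sold. Section 6.1.1 calls cinnamon a former market product with an unchanged formulation, and section 3.2.1 says it was modelled on cinnamon liquids that are on the market. This stands. A reader might infer that cinnamon falls outside the target and that only cherry and vanilla can support a conclusion about commercial products; the documents do not support that.

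A reader might also infer that the different label confounds the comparison with grape. Section 6.1.1 gives all four liquids the same 50/50 base, and section 6.1.6 gives one supplier. The outcome is change with water level, so a constant label difference cancels. Only a label that alters the response to water, or a different native water content, would bias the contrast, and neither is shown. Native water is measured (section 6.1.3), though no analysis uses it.

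The by-flavor secondary analysis is a partial answer. Section 5.2.2 says it is meant to show whether the water effect differs by aldehyde flavor, and flavor means at all four levels would make a cinnamon-driven pattern partly visible. As written, however, it compares flavors within a level and does not estimate the water effect within a flavor.

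Finally, any one of the three flavors could drive a pooled mean. That is true, and it is why the fix starts with every flavor's water effect. It is tempting to add that an unpopular flavor would be liked more when diluted and so hide a loss of appeal elsewhere. Nothing in the documents says so.

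**Conclusion.** The point holds as a modest gap between the stated goal and the analysis. Cinnamon is exactly one third of the aldehyde cells, is not currently sold and differs in label from the control. Neither planned analysis directly estimates the water effect per flavor or shows whether an aldehyde result depends on cinnamon. How often cinnamon alone would make a three-flavor contrast significant rests wholly on assumed effects: about 23% at 0.8 SD to 86% at 2.0 SD with independent flavors, and higher with correlation. The upper figures need very large effects confined to one flavor and should not be read as likely. The documents do not show that cinnamon will behave differently, nor that a result including it would be invalid for commercial products. In a 30-person pilot this is a desirable addition, not a flaw that undermines the study.

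**What to change.** 1. In section 6.5.1, fit flavor, water level and their interaction. Report the water effect for each of the four flavors, with confidence intervals, and the three-flavor aldehyde-versus-grape contrast in change from unaltered.
2. Prespecify as a sensitivity analysis the cherry-plus-vanilla versus grape contrast for gLMS irritation (all currently sold, one product line) and the cherry-plus-vanilla change from unaltered for LHS liking.
3. If these differ materially from the three-flavor result, say so when concluding about commercial e-liquids.
4. Reconcile the descriptions of cinnamon's origin in sections 3.2.1 and 6.1.1. Both could be true, but the 6.1.1 sentence is garbled and the reader cannot tell.

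No new data, participants or procedures are needed. The price is a few more estimates to report and the loss of precision in the sensitivity analysis shown above.

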3.2.2 Potential Benefits

The proposed project will provide the FDA with important data regarding how adding an innocuous constituent, water, to e-cigarettes that contain flavors chemicals comprised of aldehydes, could have the ability to reduce user' irritation. E-liquids with flavor chemicals containing aldehydes are popular and common but may have potential associated toxicity that produces user experienced irritation. Preliminary data from our chemistry lab suggests adding water may be one way to reduce potential toxicity. Regulating the level of water in e-liquids is a relatively simple regulation for the FDA to implement. However, it is possible that adding water might negatively impact the potential value of these flavors for switching from combustible cigarettes by diluting flavorants and nicotine concentrations, potentially resulting in lower delivery (and thus appeal) per puff. Study outcomes could inform potential future legislation aiming at addressing certain health concerns of vaping products, such as a mandate for a minimum amount of water present in e-liquids.

An additional benefit in this study is to participants who are current THC/CBD vapers. They may be at additional risk for EVALI given their THC/CBD vaping, but are not currently being monitored. During the study, they will be monitored for EVALI related symptoms.

4 Study Objectives

4.1 Hypothesis

We hypothesized that as total water volume is increased in nicotine e-liquids containing flavor aldehydes, sensory irritation experienced by the e-cigarette user will decrease. We do not expect to see this decrease in the control e-liquid (grape e-liquid), which does not contain flavor aldehydes.

4.2 Primary Objective

The primary objective of this study is to examine whether (a) sensory irritation and (b) appeal are decreased in e-liquids containing flavor aldehydes (i.e. vanilla, cherry, cinnamon) compared to e-liquids not containing flavor aldehydes (i.e. grape) when the water concentration is increased from the baseline water concentration to the following levels; 5% total water volume, 10% total water volume, 20% total water volume.

4.3 Secondary Objectives (if applicable)

At each water concentration, we will examine if there are differences in perception of sensory irritation and appeal across the distinct aldehyde containing flavors.

4.4 Exploratory Objectives (if applicable)

[figure not shown]
N/A

5 Study Design

5.1 General Design Description

The study is a within subjects' laboratory study, in which participants will complete two laboratory sessions under double blind conditions. Across the study, participants will be exposed to four different e-liquid flavors at a single fixed nicotine concentration (36mg/ml nicotine salt formulation). Three of the e-liquids flavors will be aldehyde containing e-liquids and one flavor will be a non-aldehyde containing flavor and serve as a control. Each flavor will be presented with the following manipulations to its water concentration; (1) flavor as commercially produced, (2) water added so 5% total water volume achieved, (3) water added so 10% total water volume achieved, (4) water added so 20% total water volume achieved. In each lab session, under double blind conditions, participants will sample two of the four flavors at each of the 4 water volumes (i.e. no change to water volume, 5% water volume, 10% water volume, 20% water volume). Participants will be randomized to flavor order and water concentration for each flavor will be presented from hypothesized least irritating to hypothesized most irritating, as is recommended with chemosensory studies.

Figure 1. Diagram of Study Procedures

5.1.1 Study Date Range and Duration

The expected duration of the total study from recruitment 2 years to complete study from HIC submission; we anticipate the subject enrollment period will be 8 months (approximately 1 week/participant). Enrollment began in August 2022, so anticipated subject enrollment will end in March 2023. The expected duration/participant is approximately 1-2 weeks to complete intake appointment(s), lab 1 and lab 2.

5.1.2 Number of Study Sites

The study will take place at Yale University School of Medicine. Study sites will include the Connecticut Mental Health Center (Rm S201) for intake appointments and Pierce Laboratories ([name]), which are equipped with ventilated research chambers utilized for smoking and vaping research studies.

5.2 Outcome Variables

The outcome variables used in this study are **irritation**, as measured by the generalized Labeled Magnitude Scale (gLMS)^{22,23} and **appeal**, as measured by the Revised Drug Effects Questionnaire²⁴ (measuring liking & stimulation), the Labeled Hedonic Scale (LHS) to measure overall liking, the gLMS to measure sweetness, and the Multiple Choice Questionnaire (MCQ; e-cig value).²⁵

5.2.1 Primary Outcome Variables

- (3)** Change in irritation at each water level
- (4)** Change in appeal at each water level

5.2.2 Secondary Outcome Variables (if applicable)

- (2)** At each water level, differences in **irritation** and **appeal** between flavors (to examine if there are differences in effect of water level on irritation/appeal by aldehyde flavor)

5.2.3 Exploratory Outcome Variables (if applicable)

N/A

5.3 Study Population

Participant will be healthy adult (21 or older) regular (at least 4x/week) e-cigarette users who are users of nicotine containing e-cigarettes (urine cotinine >200 ng/ml).

5.3.1 Number of Participants

The current study is a pilot study and we aim to enroll 30 subjects. Based on previous pilot experimental work with e-cigarettes in our group, 30 has been sufficient for by our biostatistical staff for determining large effects by water level.

5.3.2 Eligibility Criteria/Vulnerable Populations

In order to eligible to participate in the study, individuals must meet all of the follow criteria:

- At least 21 years old (legal e-cigarette use age)
- Able to read and write
- Report at least 6 months of e-cigarette use
- Report e-cigarette use at least on average 4 days/week in the past month
- Report use of flavored e-cigarettes (i.e. cannot be using unflavored e-cigarettes)
- Report use of nicotine containing e-cigarettes
- Urine cotinine levels of at least 200ng/mL
- Do not plan to discontinue e-cigarette use or other current tobacco product use (e.g. cigarettes) during study duration
- Spirometer reading with an FEV1 of $\geq 70\%$.

An individual who meets any of the following criteria will be excluded from study participation:

- Currently pregnant, breastfeeding, or trying to become pregnant
- Medical conditions including chronic and untreated acute pulmonary conditions, that in the investigators view will increase risk of respiratory problems among participants
- Known hypersensitivity to propylene glycol, vegetable glycerin, and/or e-liquid flavorants
- Current use of illegal substances, not including cannabis, as determined by both self-report and a urine drug screen at intake.
- *For current cannabis vapers:* Any report of mild or great EVALI-related symptoms (i.e. cough, shortness of breath, chest pain, nausea, vomiting, stomach pain, diarrhea, fever, chills, or weight loss) without non-EVALI reasonable and proximal cause
- Report of greater than “without any difficulty” on any item of the PROMIS Physical Function Short Form
- Any significant current medical condition such as neurological, cardiovascular, endocrine, renal, or hepatic pathology that would increase risk or would interfere with/mimic tobacco abstinence.
 - Medical conditions increasing risk of respiratory problems in nonpatient populations: Chronic Pulmonary Conditions;
 - Untreated, unresolved, acute pulmonary conditions (recurring bronchitis and Reactive airway disorder, as examples).
- Current diagnosis of an untreated psychiatric condition
- Not fully vaccinated for COVID-19

6 Methods

6.1 Treatment

6.1.1 Identity of Investigational Product

The investigational tobacco products being used in the study are the following e-liquids in 36mg nicotine salt concentration: (1) DuraSmoke Red Label (50/50 propylene glycol/vegetable glycerin base) Cherry flavor liquid, (2) DuraSmoke Red Label ((50/50 propylene glycol/vegetable glycerin base) Vanilla flavor liquid, (3) DuraSmoke Red Label ((50/50 propylene glycol/vegetable glycerin base) Grape flavor liquid, and (4) American E-liquids Store (50/50 propylene glycol/vegetable glycerin base) Cinnamon Flavor Liquid. All of these products will be administered in a Suorin iShare Pod System E-cigarette. All of these products are currently commercially available, except American E-liquids Store (50/50 base) Cinnamon Flavor Liquid, which is currently only available as a research product. However, this flavor was a previously commercially available e-liquid and was developed the formulation has not changed. It is not currently sold by American E-Liquids due to lack of popularity. In the current study, these e-liquids will be manipulated by adding water to each product, so that water concentration in each of the four flavors equals the following amounts; (1) 5% of the total e-liquid concentration, (2) 10% of the total e-liquid concentration, (3) 20% of the total e-liquid concentration. Additionally, e-liquids will be presented without added water. Participants will sample (i.e. take 2 directed puffs of each) the four flavors unaltered and in each of the listed water dilutions in randomized order. FDA has reviewed the proposed use of the products and does not have concerns with the use of the investigational tobacco products as described in the protocol. FDA issued a No Concerns letter to Investigators on 2/3/22.

6.1.2 Dosage, Administration, Schedule

6.1.3 Water Concentration Manipulation:

E-liquid water content of each e-liquid container will be quantified by Karl Fischer (KF)-titration or by gas chromatography/thermal conductivity detection (GC-TCD). Once the water content of the unaltered product has been determined, the difference to reach 5%, 10%, or 20% water content will be added to the e-liquid in question. For example, if the water content was measured at 1%, 4% will be added (all percent values are weight-based). To do so, weighed amounts of e-liquids will be added to sterile, amber glass bottles (30mL), and the appropriate amount of sterile, deionized water will be added to reach the desired water content level (5%, 10%, 20%). This preparation will take place at the Center for Green Chemistry and Green Engineering (Co-PI [name]'s lab location). The resulting 4 bottles per flavor (native water content, 5%, 10%, 20%) will then be transferred to the testing location and stored in a cool and dry location until use. For subject testing, the needed quantity of approx. 0.5mL of e-liquid will be pipetted from the storage container to the e-cigarette device for testing. 30mL of each e-liquid manipulation is sufficient to conduct procedures with all 30 anticipated pilot participants.

E-liquid Administration/Participant Instructions/Pausing due to AEs: Participants will be administered e-liquid in an observed laboratory setting in which they are instructed to take two directed puffs of each e-liquid at each water concentration. Between 2-puff puff bouts, participants will be required to wait 10-minutes before engaging in next puff bout. Participants are not allowed to leave the site with product. There will no changes in nicotine concentration (only flavor administered) and all participants will sample all flavor/water concentration manipulations. The lab sessions will be conducted by trained research staff who are sensitive to the adolescent and smoking population and trained to monitor any potential adverse effects. Heart rate, blood pressure, and pulse oximetry will be assessed at baseline and every in-person visit for safety. If they experience any side effects or concerns during the study, we ask them to let us know. Participants will be told that they are able to stop the study at any point. If they feel any discomfort or need to stop for any reason, they can let the research team know. In the event of a serious adverse event, the PI ([name]), will consult with Yale Tobacco Center for Regulatory Science (TCORS; the funder of

this pilot) co-Is, [name] [name] and [name], along with center chemosensory expert [name] to determine if blind needs to be broken. Given all study participants are administered all e-liquids, the study will be paused during this period.

